5.2.2 Treatment Group B

Subjects in Group B will have complete surgical resection of all detectable melanoma upon study entry, prior to Course 1 of hu14.18-IL2. Once the subject has recovered from the surgery (2-4 weeks, depending upon the nature of surgery (Section 4.4.8), the subject will begin Course 1 of treatment. Decisions regarding whether a subject has recovered sufficiently from surgery to begin Course 1 of treatment will be left to the discretion of the treating physician(s). To aid in this decision, laboratory tests may be ordered as warranted clinically, but no specific tests are required for this assessment. Subjects undergoing “extensive surgery” (see Section 4.4.8) will not begin Course 1 of study treatment until at least 21 days after surgery. Subjects undergoing “non-extensive surgery” will not begin Course 1 of study treatment until at least 14 days after surgery (see Section 4.4.8). No course of hu14.18-IL2 therapy will be administered sooner than 4 weeks after day 1 of the prior course of hu14.18-IL2 therapy. Subjects will receive a total of 3 courses of treatment as described in Section 5.3.

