5.4 Dose limiting toxicity and subsequent courses at reduced dose

5.4.1 Definition of DLT

The definition of DLT in this study differs from the standard definition. Dose-limiting toxicity (DLT) will be defined as Grade 3 or 4 toxicity, using the NCI Common Terminology Criteria for Adverse Events (CTCAE), version 3.0, EXCEPT as detailed below in Section 5.4.3. These toxicities will be evaluated for all subjects beginning on Course 1 day 1 during all courses of this study except for the time from the initiation of the surgical resection until recovery from surgery and initiation of Course 1 (for Group B) or Course 2 (for Group A) of protocol treatment.

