will not be considered as disease progression, and the subject can continue on study, provided the identifiable melanoma is completely resectable, and the subject has not had irreversible DLT from the protocol therapy that delays the surgery to 8 weeks after administration of cycle 1 protocol therapy.

⁶ Tumor assessment will only be done if toxicity from the surgery is so prolonged that it delays starting the second course of study therapy by 4 or more weeks from the anticipated time (post-op day 14 for non-extensive surgery or post-op day 21 for extensive surgery). If initiation of course 2 therapy is delayed by ≥ 4 weeks, radiographic assessment of tumor status is required within 2 weeks of starting Course 2 of study therapy.

TABLE 6B.

CLINICAL ASSESSMENT GUIDELINES FOR THE SURGICAL RESECTION AND POST-OP PERIOD: GROUP B (SURGERY BEFORE COURSE 1 OF STUDY THERAPY)

	Pre-Operative¹	Immediate Post-operative²	≤ 1 week before starting hu14.18-IL2³
Physical Exam		X	X
Weight	X	X	X
Performance Status	X		X
Tumor Assessment			X⁴
Vital signs (T, BP, P, RR)	X	X	X
CBC, diff, plts			X
AST, ALT, T bili, alk phos, alb, LDH, Na, K, Cl, HCO ₃ , Cr, BUN, Glucose, Ca, Mg, Phosphate			X
INR/PTT			X
Urinalysis			X

¹ The pre-operative studies indicated here can be done the day of or the day before surgery

² Post-operative management and tests required should be those felt to be needed for patient care by the surgical team.

³ The exact tests to be ordered will be left to the discretion of the treating physician(s) as they are warranted clinically to assess recovery from surgery. It is anticipated that these tests will be obtained 1-3 weeks post-operatively, depending on the nature and extent of the surgery, and the post-operative recovery. If the results of these tests suggest the subject has not fully recovered from surgery, additional clinical evaluation may be required to identify the cause of the abnormality and to provide treatment if indicated. Tests may be repeated as needed until adequate resolution so the patient may begin Course 1 of hu14.18-IL2, preferably within 4 weeks of surgery. If 8 weeks pass post-operatively, and the treating physician(s) still feel(s) that the subject is not fit to continue, the subject will not receive hu14.18-IL2.

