6	0.38	0.21	0.58
8	0.50	0.31	0.69
10	0.62	0.42	0.79
12	0.75	0.55	0.88
14	0.88	0.68	0.96

Therefore, with a sample size of 16 subjects, the 90% confidence interval for the two-year survival/two-year recurrent-free survival rate will be no wider than 38%.

Secondary endpoints of this pilot study include adverse events, immunological parameters, density & phenotype of cellular infiltrate and expression of GD2 target antigen, and IFN- γ expression. Assuming a total sample size of 16, the probability of observing at least one incidence of Grade ≥ 3 toxicity is 81%, if the true toxicity rate is 10%. Analogously, the probability of observing at least one incidence of Grade ≥ 3 toxicity is 93%, if the true toxicity rate is 15%. Immunological parameters will be measured on a continuous scale. Assuming a sample size of eight subjects per

study arm, a difference of 1.5 standard deviation units in magnitude will be detected with 80% power at a two-sided significance level of 0.05 (based on a two-sample t-test). A difference of only 1.25 standard deviation units will be detected with 63%. Smaller differences are unlikely to be detected as statistically significant.

In order to account for “unevaluable” subjects and drop-outs (e.g., patients without an evaluation following course 2 of IC treatment), we will accrue up to 20 eligible subjects (10 per arm) in total. Based on our past experience with advance melanoma subjects treated at UWCCC, we expect to accrue 20 eligible subjects within 24 months. The minimum follow-up period will be 12 months after the last subject has entered the study.

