9.4.9 Stopping rules for excessive toxicity

Many of the dose limiting toxicities (DLTs) that occur due to hu14.18-IL2 therapy are not unexpected. However, a subset of the DLTs described in Section 5.0 of the protocol are considered unacceptable. Those DLTs are:

1. Toxicity requiring the use of vasopressors, including Grade 4 vascular leak syndrome and/or grade 4 hypotension, and
2. Toxicity requiring ventilatory support, including Grade 4 respiratory toxicity.

If at any time a patient requires ventilatory support, new accrual to the study will be temporarily stopped, and the study will be reviewed for safety, dose modification and safety modification.

[figure not shown]
Based on this, a decision regarding reopening the study, likely with an appropriate amendment, would be made by the DSMC, working with the study committee.

Furthermore, accrual to this study will be temporarily suspended at any stage during the accrual period if an excessive toxicity rate is observed. An excessive toxicity rate is defined as follows:

1. At least 15% for Grade 4 vascular leak syndrome or grade 4 hypotension toxicities, or
2. At least 33% for any Grade 4 DLTs.

Evidence that the toxicity rate is excessive will be considered sufficient if the lower limits of the 90% one-sided confidence intervals for the estimates of the true toxicity rates exceed the toxicity limits defined above (i.e., 15% for Grade 4 vascular leak syndrome or hypotension, 33% for any grade 4 DLTs).

Operationally, this will occur if any of the following events occur: Grade 4 vascular leak syndrome or Grade 4 hypotension toxicities are present in at least 2 out of 3 (or less) patients, 3/7, 4/12, 5/17, or 6/20 of the patients accrued, or if any Grade 4 DLTs are present in at least 3 out of 3, 4/6, 5/8, 6/10, 7/13, 8/15, 9/17, or 10/20 of the patients accrued. If one of these thresholds is reached, accrual will be temporarily suspended and the study will be reviewed for safety, dose modification and safety modification. The study would only be reopened if modifications can be made, and approved by the DSMC and the UW-IRB, to assure that patient safety is reestablished. If not, the study would be closed. The stopping rule is illustrated in the following figure:

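### The stopping rule in Section 9.4.9 counts patients accrued, not patients dosed, so one undosed patient can keep it from firing at a boundary; it also leaves open whether Grade 5 events count

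*Combined protocol and SAP*

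**What the plan says.** Section 9.4.9 sets two limits for an excessive toxicity rate: "At least 15% for Grade 4 vascular leak syndrome or grade 4 hypotension toxicities" and "At least 33% for any Grade 4 DLTs". The evidence required is that the "lower limits of the 90% one-sided confidence intervals for the estimates of the true toxicity rates exceed the toxicity limits defined above". The section then turns this into event counts. For the 15% limit the list is 2 out of 3 (or fewer), then "3/7, 4/12, 5/17, or 6/20 of the patients accrued". For the 33% limit it is 3/3, 4/6, 5/8, 6/10, 7/13, 8/15, 9/17 and 10/20, again of patients accrued.

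Other sections show that accrued and dosed are not the same:

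- **Section 5.2.2:** the surgery-first arm is operated on at entry. After extensive surgery a subject "will not begin Course 1 of study treatment until at least 21 days after surgery"; after non-extensive surgery the minimum is 14 days. (This arm is Group B in Sections 5 to 7. Section 9.3 swaps the letters, but one arm waits under either labelling.)
- **Section 7.2, Table 6B, footnote 3:** a subject in that arm still judged unfit 8 weeks after surgery leaves the treatment path: "the subject will not receive hu14.18-IL2".
- **Section 9.3.2:** to cover unevaluable subjects and drop-outs, "we will accrue up to 20 eligible subjects (10 per arm) in total".
- **Section 5.4.1:** toxicities are assessed for DLT from Course 1 day 1, and "Dose-limiting toxicity (DLT) will be defined as Grade 3 or 4 toxicity".

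Section 14.1.1 records Grade 3, 4 and 5 toxicities from randomization.

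**The concern.** A patient who has had no hu14.18-IL2 cannot have a toxicity from it, and Section 5.4.1 does not open the DLT window until the first dose. Such a patient adds to the denominator and can never add to the numerator while undosed. A patient waiting for surgical recovery does this for some weeks; a patient who is never dosed does it permanently. If the fractions are tight against the confidence criterion, even one such patient could let accrual continue when the criterion, applied to patients at risk, is met. With at most 20 patients, a denominator wrong by one matters.

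The second question is about the numerator. Both limits and both lists name Grade 4, and the DLT definition names Grade 3 or 4. On the literal wording, a fatal vascular leak or hypotension event enters neither count.

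**Working it through.** **1. Reproduce the plan's boundaries.** Inputs from Section 9.4.9: limits of 15% and 33%, one-sided 90% confidence. For x events in n patients the exact (Clopper-Pearson) lower limit is the 10th percentile of a Beta(x, n − x + 1) distribution. It exceeds p0 exactly when P(X ≥ x | n, p0) < 0.10. Taking, for each x, the largest n up to 20 that satisfies this returns all 13 listed fractions. The Wilson, Wald, Jeffreys, Agresti-Coull and mid-P limits do not reproduce both lists. The plan's fractions are therefore right, and each is the last n at which its event count triggers suspension.

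**2. Add one undosed patient.** Example at p0 = 0.15:

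- n = 7: P(X ≥ 3) = 1 − (0.85^7 + 7 × 0.15 × 0.85^6 + 21 × 0.15² × 0.85^5) = 1 − (0.3206 + 0.3960 + 0.2097) = 0.074, below 0.10, so suspend.
- n = 8: P(X ≥ 3) = 1 − (0.85^8 + 8 × 0.15 × 0.85^7 + 28 × 0.15² × 0.85^6) = 1 − (0.2725 + 0.3847 + 0.2376) = 0.105, above 0.10, so continue.

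Lower limits at each boundary below n = 20:

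| Limit | Dosed denominator | Lower limit | One undosed patient added | Lower limit |
|---|---|---|---|---|
| 15% | 2/3 | 19.6% | 2/4 | 14.3% |
| 15% | 3/7 | 17.0% | 3/8 | 14.7% |
| 15% | 4/12 | 15.4% | 4/13 | 14.2% |
| 15% | 5/17 | 15.1% | 5/18 | 14.2% |
| 33% | 3/3 | 46.4% | 3/4 | 32.1% |
| 33% | 4/6 | 33.3% | 4/7 | 27.9% |
| 33% | 5/8 | 34.5% | 5/9 | 30.1% |
| 33% | 6/10 | 35.4% | 6/11 | 31.8% |
| 33% | 7/13 | 33.1% | 7/14 | 30.5% |
| 33% | 8/15 | 34.2% | 8/16 | 31.8% |
| 33% | 9/17 | 35.0% | 9/18 | 32.9% |

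All eleven decisions reverse. The 6/20 and 10/20 boundaries are not affected, because accrual is capped at 20.

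**3. How many patients are waiting?** Section 9.3.2 expects 20 patients in 24 months, so the surgery-first arm enters 20/24/2 = 0.417 per month. At 4.345 weeks per month, the expected number waiting is 0.417 × 2/4.345 = 0.19 for a 2-week wait, 0.38 for 4 weeks and 0.77 for 8 weeks. Never-dosed patients come on top.

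**4. Effect on the chance of suspending.** Assumptions for the simulation: 20 patients enter uniformly over 24 months, 10 per arm; the drug-first arm is dosed 7 days after entry and the surgery-first arm 21 to 42 days after entry; events are equally likely in Courses 1 to 3. The never-dosed fraction is also assumed.

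| Never dosed | 15% rule, true rate 30%: dosed v accrued | 33% rule, true rate 50%: dosed v accrued |
|---|---|---|
| None | 70% v 68% | 68% v 66% |
| 10% of surgery-first arm | 67% v 63% | 64% v 58% |
| 20% of surgery-first arm | 67% v 57% | 62% v 50% |

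Counting only events during accrual, with nobody undosed, gives 64% v 61% and 60% v 57%. The levels shift by some points with the timing assumptions; the pattern does not.

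**5. Grade 5 on the literal wording.** If one of the events is fatal and is not counted, 2/3 (19.6%) is scored 1/3 (3.5%), 3/7 (17.0%) is scored 2/7 (7.9%), and 4/6 (33.3%) is scored 3/6 (20.1%). Each moves from suspend to continue.

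**The case against.** **The intent can be inferred.** The criterion speaks of true toxicity rates and the DLT window opens at the first dose, so a careful reader might count dosed patients anyway. That supports the correction, but the operational sentence is what staff will apply, and it says accrued.

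**The effect is small on what the documents establish.** This stands. Waiting alone costs about 2 to 3 points, and fewer than one patient is expected to be waiting at a time. One undosed patient matters only when the count sits exactly on a boundary. A reader might infer much larger losses: spreading a 20% never-dosed fraction over both arms gives 62% v 44% for the 15% rule and 60% v 34% for the 33% rule. The documents do not support that scenario. They give no never-dosed fraction, and the only explicit route to never being dosed (Table 6B, footnote 3) is in the surgery-first arm. Failed resection in the drug-first arm comes after Course 1, and the unevaluable subjects in Section 9.3.2 may well have been dosed.

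**Deaths are not ignored.** This also stands. Any ventilatory support stops new accrual under Section 9.4.9. Section 14.2 requires expedited reporting of deaths within 30 days of the last dose, Section 13.3.1 takes reports due within 24 hours to the DSMC within one working day, and Section 13.3.3 lets the DSMC recommend suspension. A fatal course with a recorded Grade 4 event on the way may already be counted. These safeguards are discretionary or partial, and none says how a Grade 5 event enters the fractions.

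**Conclusion.** The denominator point holds. Section 9.4.9 states an exact criterion and then applies it to a count that includes patients not at risk. At all eleven boundaries below n = 20, one such patient takes the lower limit under its threshold. The size is modest: about 2 to 3 points in the chance of suspending if everyone is eventually dosed, and about 4 to 12 points if 10% to 20% of the surgery-first arm are never dosed. The second range rests on an assumed fraction and on the timing assumptions shown.

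The Grade 5 point is a separate gap in wording. A reader might infer that leaving out deaths also makes accrual continue against the rule's own criterion. It does not: the criterion is itself limited to Grade 4, so criterion and counts agree, and both are silent on Grade 5. Nor do the documents show that a single death must pause accrual; that is for the study team and the DSMC to decide.

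**What to change.** In Section 9.4.9, change the denominator in both operational lists from patients accrued to *patients who have received at least one dose of hu14.18-IL2*. Keep every fraction, since all are correct for that denominator. This needs no new data; the downside is that accrual may pause slightly more often.

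Separately, reconcile Section 9.4.9 and the DLT definition in Section 5.4.1 with the recording of Grade 5 toxicities in Section 14.1.1, and state whether a Grade 5 event counts with Grade 4 toward each limit. This costs a sentence.

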10.0 EVALUATION AND MANAGEMENT OF TOXICITY AND SUPPORTIVE CARE

10.1 Grading of toxicity and dose modification

Grading of toxicities on this study will be with NCI CTC, version 3.0. All significant adverse events will be followed until they resolve to baseline or < Grade 2, or are deemed irreversible.

10.1.1 Dose modification for DLT

Dose limiting Toxicity (DLT) criteria and exclusions are described in protocol section 5.3. For any occurrence of DLT, treatment with protocol therapy will be stopped. Treatment may not be resumed until after toxicity has resolved to meet original eligibility criteria. Resuming treatment following any DLT at a reduced dose (according to the guidelines below) requires contact (by phone or e-mail) with the FDA on a case-by-case basis. The first contact will be to the FDA Oncology Drug Products review division in the Center for Drug Evaluation and Research at [contact]. An alternate contact is at the following: [contact]; [contact], [contact].

For toxicities occurring during treatment with hu14.18-IL2, if DLT occurs on day 1 or 2 of any course, treatment can only be resumed during that same course (i.e., on day 2 or 3) at 50% of the starting dose, and only if the toxicity has resolved to meet eligibility criteria in time to give the day 2 or day 3 dose on schedule. If eligibility criteria are not met in time to receive additional therapy during the course in which the toxicity occurred, but are met in time to start the next course (i.e., day 1 +/- 7 days), treatment will resume at 50% of the dose associated with the DLT. Any planned drug administration that is withheld due to DLT will not be given on a delayed schedule to “make up” for missed drug. If toxicity again requires treatment cessation, treatment can be restarted at 25% of initial treatment dose. If treatment at this reduced dose results in recurrence of DLT or significant non-DLT toxicity, treatment will be permanently discontinued. Treatment will be resumed, as described above, using only 50% of the starting dose of hu14.18-IL2, and only if the toxicity has resolved to meet eligibility criteria.

10.1.2 Dose modification for toxicity that is not graded as DLT

It is the intention of this pilot study to treat all patients, at all courses, at the starting doses of 6 mg/m²/d for hu14.18-IL2, or the maximum dose that each patient demonstrates is tolerable for them. However, if severe toxicity is observed, such that the investigator feels discontinuation of treatment at the dose level causing the toxicity is in the patient’s best interest, temporary or permanent cessation of treatment at that dose level, or a 50% dose reduction for subsequent infusions (in the absence of DLT) is permissible. Justification for discontinuation of therapy or dose reduction must be clearly documented. At no time will the dose level be escalated.

10.2 Supportive care

10.2.1 Hematologic toxicity

All subjects will be transfused as needed to maintain an adequate Hgb level (≥ 8.0) and platelet count ($\geq 40,000$) during Days 1-3 of treatment each month. Hematologic DLT criteria are detailed in Section 5.3. As there may be an association of vascular leak syndrome with co-administration of monoclonal antibody-IL2 and transfusions, it is recommended to avoid transfusions during the 3 days of hu14.18-IL2 administration, and particularly during the daily 4-hour infusions. If transfusions are needed, it is recommended that they be given at least 12 hours before starting treatment on day 1 of each course and > 12 hours after finishing the day 3 infusion. If transfusions must be given on day 3 to maintain Hgb >8.0 and plts > 40,000, these should be given 12 hours after completing the prior 4-hr infusion of hu14.18-IL2. If the subject experiences neutropenia (ANC < 1000) while receiving the fusion protein, treatment would not be interrupted since neutropenia is common and rapidly reversible upon stopping IL2 treatment. For days 8-29 of each course of therapy, transfusions should be given, if needed, to maintain a platelet count of >20,000, and a Hgb of > 7.0.

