5.4.3 Detailed listing of DLT exceptions

The following toxicities will be graded and recorded, but will not be used as criteria for determining DLT:

- a) Grade 3 pain, requiring intravenous narcotics, provided that the narcotics are controlling the pain, and that IV narcotics for pain are not required > 48 hours after completion of hu14.18-IL2 on Day 3 of any treatment course;
- b) Grade 3 nausea and vomiting that resolves within 48 hours after completion of hu14.18-IL2 on Day 3 of any treatment course;
- c) Grade 3 fever (i.e., T > 40° C) lasting < 6 hours and controllable with antipyretics;
- d) Grade 3 skin toxicity that improves with treatment (e.g., IV Benadryl) within 24 hrs;
- e) Grade 3 metabolic/laboratory toxicity of hyponatremia, hyperglycemia, or hypophosphatemia in the absence of CNS symptoms and/or sequelae, that improves with or without treatment within 48 hrs;
- f) Grade 3 sensory or motor peripheral (non-cranial) neuropathy (i.e., interference with function plus objective weakness) if transient and reversing within 3 days of completion of hu14.18-IL2 of any treatment course. Subjective findings (e.g., tingling, hot/cold hands) are expected and will not be DLT;
- g) Grade 3 hematologic toxicity (or grade 4 lymphopenia – a known transient marker of immune activation by IL2) which improves to at least Grade 2 or pre-therapy baseline values without requiring transfusion within one week of completion of hu14.18-IL2 of any treatment course (see Section 10.2.1 for management of hematologic toxicity and transfusion guidelines);
- h) Grade 3 infusional reactions lasting less than 24 hours, readily controlled with supportive (non-steroidal) treatments (i.e., Benadryl) and not requiring epinephrine;
- i) Grade 3 fatigue or ECOG performance status that resolves in ≤ 1 week;
- j) Grade 3 infection that resolves in ≤ 1 week.

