The above dose limiting toxicity exceptions are based on the known, published, transient, reversible toxicities of IL2 and hu14.18. These toxicities may be expected, based on observations of hu14.18-IL2 given to 33 + 14 (phase I and II respectively) adults with melanoma, administered by the same schedule at similar doses to that being tested in this trial, and will not require interruption, modification, or discontinuation of treatment. In our experience with hu14.18-IL2 in adults with melanoma, asymptomatic hypophosphatemia is a relatively frequent occurrence. Therefore, all subjects scheduled to receive this agent will be given oral phosphate supplementation prophylactically starting on day 1 and ending on day 8 of each course (see Section 10.3.4.3 for details). **All grade 4 toxicities (except for transient lymphopenia) are considered as DLT and require stopping treatment with hu14.18-IL2. Following resolution of a DLT, and if subsequent hu14.18-IL2 treatment is given, it must be given at a reduced dose.**

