5.4.4.1 Dose-reduction plan for hu14.18-IL2

For toxicity associated with hu14.18-IL2, there must also be consideration of the schedule of administration. If this toxicity occurs on day 1 or 2 of any course, treatment can be resumed during that same course (i.e., on day 2 or 3) at 50% of the starting dose only if the toxicity has improved to meet eligibility criteria in time to give the day 2 or day 3 dose on schedule. If eligibility criteria are not met in time to receive additional therapy during the course in which the toxicity occurred, but are met in time to start the next course (i.e., day 1 of the next course +/- 7 days), treatment will resume at 50% of the dose that caused the DLT. If toxicity again requires treatment cessation, treatment can be restarted at 25% of initial treatment dose. If treatment at this reduced dose results in recurrence of DLT or significant non-DLT toxicity, treatment will be permanently discontinued.

Repeat lab testing will be done weekly until eligibility criteria are met, and treatment will begin at 50% of the prior dose. If after 4 additional weeks of testing, eligibility criteria still are not met, the subject will not be eligible for any additional treatment with the study agent responsible.

Subjects with Grade 4 toxicity related to protocol treatment (other than transient lymphopenia from hu14.18-IL2, see Section 5.3.3.g) will not receive additional protocol treatment during that treatment course. Patients experiencing Grade 4 neutropenia or leukopenia that lasts \leq 4 days; Grade 4 thrombocytopenia that can be corrected with platelet transfusion (see Section 10.2.1); or Grade 4 nausea, vomiting, anorexia or fatigue lasting less than 2 days, and resolves to meet eligibility criteria, may be eligible to receive continued study therapy (provided that all other criteria for continued treatment are met) at 50% of the dose received prior to the onset of this toxicity. Subjects with any other Grade 4 toxicity related to the protocol treatment will not receive additional protocol treatment during that course and will be withdrawn from the study. Subjects experiencing Grade 4 events that are clearly unrelated to the study treatment, last \leq 3 days, and improve to meet eligibility criteria, may be eligible to receive continued study therapy (provided that all other criteria for continued treatment are met) at 50% of the daily dose received prior to the onset of this toxicity.

[figure not shown]

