7.2 Clinical Assessment

The detailed schedules for treatment administration and clinical monitoring are included below in Tables 5, 6A, and 6B.

TABLE 5. CLINICAL ASSESSMENT FOR EACH TREATMENT COURSE

DAY	Base Line ²	Week 1						Weeks 2-4	Week 5 ¹
		1	2	3	4			8	29/1 ¹
Hu14.18-IL2		X	X	X					X
Complete history/PE	X								
Physical Exam		X	X	X					X ³
Adverse event assessment		X	X	X	X			X	X ³
Weight	X	X	X	X	X			X	X ³
Performance Status	X	X	X	X	X			X	X ³
Pregnancy Status	X								
ECG	X								
Tumor Assessment	X ⁶								X ⁴
Vital signs (T, BP, P, RR)	X	X ^{5,6}	X ^{5,6}	X ^{5,6}	X			X	X ³
CBC, diff, plts	X			X				X	X ³
AST, ALT, T bili, alk phos, alb, LDH, Na, K, Ca, Mg, Cr, BUN, CRP ⁷	X			X				X	X ³
Serum phosphate ⁸ and glucose ⁹	X			X				X	X ³
INR/PTT	X			X					X ³
Urinalysis	X								X ³
Hgb A1C, TSH	X								
HIV/HBsAg	X								
Head MRI or Head CT	X								
Biopsy	X ¹⁰								

¹ Day 29 of each course (+/- 7 days leeway to facilitate clinical scheduling) = day 1 of subsequent course.

² Baseline tests/exams, with the exception of laboratory assessments, may be performed on or before day 1 but must be performed ≤ 3 weeks prior to randomization. Laboratory assessments must be done ≤ 2 weeks prior to randomization.

³ These tests may be performed up to 1 week prior to initiating the next course of therapy, or day 22-29 of the present course if no more study therapy is to be administered.

⁴ Tumor assessments will take place at baseline and after Course 2. (Long-term follow-up will include further tumor measurements; see Table 8.) The assessment after Course 2 will be performed no earlier than day 8, but can be performed out to day 29 (+/- 7 days leeway to facilitate clinical scheduling), thus allowing adequate time to obtain biopsies of any questionably recurrent disease to determine if the subject is eligible to continue on study (see Section 5.3.1.3 for details regarding these biopsies). Baseline radiological evaluation will include CT scans of the chest, abdomen, and pelvis, and head MRI. Assessments after Course 2 and during long-term follow-up will include CT scans of areas of known prior disease. Other examinations can be performed as warranted clinically. Consistency will be maintained in the imaging modality used to measure tumor while patient is on study.

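### Section 10.2.1 continues dosing through neutropenia with no lower ANC limit, which contradicts the Grade 4 stopping rules in 5.4.3, 5.4.4.1 and 10.1.1

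*Combined protocol and SAP*

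**What the plan says.** Section 10.2.1, under supportive care, gives this instruction on neutropenia: "If the subject experiences neutropenia (ANC < 1000) while receiving the fusion protein, treatment would not be interrupted". The reason given is that neutropenia is common and reverses quickly once IL2 is stopped. Earlier in the same paragraph it refers the reader elsewhere for the DLT rules: "Hematologic DLT criteria are detailed in Section 5.3".

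The treatment plan and the dose-modification section say the following.

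- **5.4.3, item g.** Grade 3 hematologic toxicity, or Grade 4 lymphopenia, is not a DLT if it "improves to at least Grade 2 or pre-therapy baseline values without requiring transfusion within one week of completion of hu14.18-IL2". The item then refers the reader to 10.2.1 for managing hematologic toxicity.
- **5.4.3, closing text.** "All grade 4 toxicities (except for transient lymphopenia) are considered as DLT and require stopping treatment with hu14.18-IL2".
- **5.4.4.1.** A subject with related Grade 4 toxicity other than transient lymphopenia "will not receive additional protocol treatment during that treatment course". It then names the event directly: "Patients experiencing Grade 4 neutropenia or leukopenia that lasts" 4 days or less, and resolves to eligibility, may allow later therapy at 50% of the prior dose.
- **10.1.1.** "For any occurrence of DLT, treatment with protocol therapy will be stopped". Resuming at a reduced dose requires case-by-case contact with the FDA.

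**The concern.** The 10.2.1 instruction covers every ANC below 1000 during dosing. For a subject with Grade 4 neutropenia, one section says to carry on and three say to stop. The protocol does not state which prevails.

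A clinician who follows 10.2.1 would give the next full-dose infusion to a subject who, under the treatment plan, should receive nothing more in that course. The FDA contact that 10.1.1 requires before retreatment after a DLT would also be bypassed. The reason offered in 10.2.1 does not support this, because recovery after IL2 is stopped is no argument for giving another dose at Grade 4.

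**Working it through.** The main check is a comparison of rules. A short calculation then sizes the exposure.

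**Step 1: does Grade 4 fall inside the 10.2.1 wording?** Table 3 in Section 1.3.5 (Phase I laboratory changes, graded by CTC version 2.0) labels ANC 1000–1499 as grade 2 and ANC below 1000 as grade 3. This trial grades by version 3.0, and the documents give no Grade 4 cut-off for ANC. None is needed. Section 5.4.4.1 treats Grade 4 neutropenia as a category of its own, Grade 4 is a lower count than Grade 3, and 10.2.1 has no floor. Grade 4 is therefore included.

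**Step 2: what does each section require?**

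| Event during dosing | 10.2.1 | 5.4.3 | 5.4.4.1 | 10.1.1 |
|---|---|---|---|---|
| Grade 3 neutropenia recovering within a week without transfusion | Continue | Not a DLT (item g) | Not triggered | Not triggered |
| Grade 4 neutropenia | Continue | DLT, stop | No more dosing that course; later 50% if it lasted 4 days or less and eligibility is met | Stop |

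The first row is consistent. The second is not.

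Section 10.1.1 does allow resumption within a course at 50% once a DLT has resolved to eligibility, whereas 5.4.4.1 does not allow this after Grade 4. Both require stopping first, so neither fits an instruction not to interrupt.

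**Step 3: how much dosing is exposed?** Table 5 ("CLINICAL ASSESSMENT FOR EACH TREATMENT COURSE") schedules the in-course CBC on days 3 and 8. Infusions are on days 1, 2 and 3, so none remains by day 8. On the scheduled counts, the exposed dose is the day 3 infusion: 6 / (3 × 6) = 6/18 = 0.33 of a course.

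**Step 4: how often might it arise?** The Table 3 denominators by dose level are:

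- Course 1: 3 + 6 + 6 + 6 + 6 + 6 = 33
- Course 2: 2 + 6 + 1 + 5 + 3 + 2 = 19

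ANC below 1000 occurred in 0/33 and 0/19. Section 1.3.5 also reports no Grade 4 toxicity of any kind. With zero events, the one-sided 95% upper bound is 1 − 0.05^(1/n):

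- All doses, course 1: n = 33, 1 − 0.05^(1/33) = 0.087
- 6.0 and 7.5 mg/m², course 1: n = 6 + 6 = 12, 1 − 0.05^(1/12) = 0.221

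These bounds are for any ANC below 1000. The Grade 4 rate cannot exceed that rate and is expected to be well below it.

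**Step 5: is the toxicity stopping rule affected?** No. Section 9.4.9 counts Grade 4 DLTs, and Grade 4 neutropenia is a DLT under Section 5.4 whether or not dosing continued.

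**The case against.** The best defence is that 10.2.1 is a supportive-care sentence that was only ever meant for Grade 3. Its threshold is the one Table 3 labels grade 3, and read that way it restates item g of 5.4.3. The DLT rules are more prominent, and 5.4.4.1 names the exact event. The pointer to Section 5.3 is also not a dead end: 5.3 itself stops infusions for DLT and refers on to 5.4 and 5.4.4. The wrong section number recurs elsewhere in the protocol and looks like stale numbering. A dose-modification figure cited in 5.4.4 is not visible in the text reviewed.

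On size, harm needs Grade 4 neutropenia by day 3, a result available before the infusion, and a clinician who overlooks several stop rules. The physician may also stop for non-DLT toxicity. The completed Phase II trial treated 14 patients at this dose and reported no protocol-defined DLTs, although its DLT definition is not given here. The 8.7% and 22.1% bounds do not measure Grade 4 directly.

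Much of this stands. Grade 3 is very probably what was intended, and the event should be rare. The contradiction remains, however. No precedence is stated, and item g of 5.4.3 sends the reader to 10.2.1 for hematologic management. Following the pointer back through 5.3 reaches the opposing rule without reconciling the two. The figure, whatever it shows, would not remove the 10.2.1 sentence.

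**Conclusion.** The concern holds, at minor severity. As written, 10.2.1 cannot be followed together with 5.4.3, 5.4.4.1 and 10.1.1 when neutropenia is Grade 4. The conflict is limited to the remaining infusions of the same 3-day course, and endpoints, sample size and analysis are untouched. The conclusion assumes only that Grade 4 neutropenia means a lower ANC than Grade 3. The small practical size assumes that counts follow the Table 5 schedule and that Phase I experience carries over. An extra count drawn on clinical grounds before day 3 could also bring the day 2 infusion into question.

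**What to change.** In 10.2.1, restrict the neutropenia sentence to Grade 3. Add that Grade 4 neutropenia is handled under 5.4.3 and 5.4.4.1: no further infusion in that course, then 50% of the prior dose if it lasted 4 days or less and the eligibility criteria are met again. Change the pointer for hematologic DLT criteria from Section 5.3 to Section 5.4.

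The cost is one sentence of protocol wording and one section number. Design, sample size and visits do not change.
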